### **3.1.2. Clinical Safety Laboratory Tests**

Safety laboratory tests will be performed at the times specified in the Schedule of Activities in the protocol.

Baseline will be defined as the last non-missing pre-dose measurement for each period.

Any clinical laboratory abnormalities of potential clinical concern will be described. To determine if there are any clinically significant laboratory abnormalities, the haematological, clinical chemistry, urinalysis and other safety tests will be assessed against the criteria specified in the sponsor reporting standards. The assessment will take into account whether each participant's baseline test result is within or outside the laboratory reference range for the particular laboratory parameter.

### **3.1.3. Vital Signs**

Supine blood pressure (BP) and pulse rate measurements will be taken at the times specified in the Schedule of Activities in the protocol. Orthostatic BP and pulse rate measurements will also be taken at additional times specified in the Schedule of Activities in the protocol. Note that some of the supine BP and pulse rate measurements are collected as part of the orthostatic assessment.

Baseline will be the Pre-Dose (0 hour) assessment on Day 1 of each period.

The following endpoints will be determined:

- Postural differences (supine - standing) for systolic and diastolic BP (at each orthostatic assessment timepoint)
- Postural differences (standing – supine) for pulse rate (at each orthostatic assessment timepoint)
- Change from baseline in supine, standing and postural differences for systolic and diastolic BP and for pulse rate
- The minimum and maximum post-dose supine and standing for systolic and diastolic BP and for pulse rate
- The maximum post-dose postural differences for systolic and diastolic BP and for pulse rate
- The maximum decrease and increase from baseline over all measurements taken post-dose for supine, standing and postural differences for systolic and diastolic BP and pulse rate.

The maximum increase from baseline will be calculated by selecting the maximum change from baseline over the respective period, except in the case where a participant does not show an increase. In such an instance, the minimum decrease should be taken. Similarly, the maximum decrease from baseline will be determined by selecting the minimum value of the changes from baseline. In cases where a participant does not show a decrease, the minimum increase should be taken.

### 3.1.4. Continuous Cardiac Monitoring

Continuous cardiac monitoring will be performed using telemetry as outlined in the protocol.

All abnormal rhythms will be recorded and reviewed by the investigator for the presence of rhythms of potential clinical concern. The time, duration, and description of the clinically significant event will be recorded in the CRF. Events deemed of clinical concern will be recorded as AEs and will be summarized as part of the standard AE outputs.

### 3.1.5. 12-lead Electrocardiograms

A single 12-lead ECG will be obtained on all participants at screening. 12-lead ECGs will be recorded in triplicate on all participants at all other times detailed in the Schedule of Activities in the protocol.

The QT, QTcF, PR, RR, QRS complex and heart rate will be recorded at each assessment time. If not supplied, QTcF will be derived using Fridericia's heart rate correction formula:

$$QTcF = QT / (RR)^{1/3} \quad \text{where RR} = 60/\text{HR} \text{ (if not provided).}$$

The average of the triplicate readings collected at each assessment time will be calculated for each ECG parameter. Baseline will be the average of the triplicate ECG measurements collected at the pre-dose (0 hour) assessment on Day 1 of each period.

The following endpoints will be determined:

- Change from baseline in QT, QTcF, PR, QRS complex and heart rate
- The maximum post-dose QTcF, PR and QRS complex
- The maximum increase from baseline over all measurements taken post-dose for QTcF, PR and QRS values

The maximum increase from baseline will be calculated by selecting the maximum change from baseline over the respective period, except in the case where a participant does not show an increase. In such an instance, the minimum decrease should be taken.

### 3.1.6. Respiratory Rate

Respiratory rate will be measured at times specified in the Schedule of Activities in the protocol.

Baseline will be the Pre-Dose (0 hour) assessment on Day 1 of each period.

Change from baseline in respiratory rate will be determined, as well the maximum increase and decrease from baseline over all measurements taken post-dose.

### 3.1.7. Oral Body Temperature

Oral body temperature will be measured at times specified in the Schedule of Activities in the Protocol.

Baseline will be the Pre-Dose (0 hour) assessment on Day 1 of each period.

Change from baseline in body temperature will be determined, as well the maximum increase and decrease from baseline over all measurements taken post-dose.

### 3.1.8. Physical and Neurological Examination

*Medical history, physical examination, and neurological examination information, as applicable, collected during the course of the study will be considered source data and will not be required to be reported, unless otherwise noted. However, any untoward findings identified on physical and/or neurological examinations conducted during the active collection period will be captured as AEs, if those findings meet the definition of an AE.*

### 3.2. Secondary Endpoint(s)

The secondary endpoints are the following PK parameters, derived from the plasma PF-07258669 concentration-time profiles, if data permit, using standard non-compartmental methods and actual PK sampling times:

- $C_{max}$ ,
- $AUC_{last}$ ,
- $AUC_{inf}$ ,
- $T_{max}$ ,
- $t_{1/2}$ .

Blood samples for PK analysis of plasma PF-07258669 will be collected according to the Schedule of Activities in the protocol.

Further definitions and details can be seen in [Appendix 1](#).

Table 2 shows the analysis scale and method.

**Table 2. Non-compartmental PK Parameters**

Parameter	Analysis Scale	PF-07258669
$AUC_{inf}^*$	ln	D
$AUC_{last}$	ln	D
$C_{max}$	ln	D
$T_{max}$	R	D
$t_{1/2}^*$	R	D

Key: D=displayed with descriptive statistics, ln=natural-log transformed,

R=raw (untransformed), \*=if data permit

CCI

CCL

CCI

CCI

CCI

[figure not shown]
CCI

CC1

CCI

CCI

### 3.4. Safety Endpoints

Safety Endpoints are described in Section 3.1.

## 4. ANALYSIS SETS (POPULATIONS FOR ANALYSIS)

Data for all participants will be assessed to determine if participants meet the criteria for inclusion in each analysis population prior to unblinding and releasing the database and classifications will be documented per standard operating procedures.

For purposes of analysis, the following analysis sets are defined:

Participant Analysis Set	Description
Enrolled/Randomly assigned to study intervention	"Enrolled" means a participant's, or their legally authorized representative's, agreement to participate in a clinical study following completion of the informed consent process. Potential participants who are screened for the purpose of determining eligibility for the study, but do not participate in the study, are not considered enrolled, unless otherwise specified by the protocol.
Evaluable	All participants randomly assigned to study intervention and who receive a dose of study intervention.
Safety	All participants randomly assigned to study intervention and who receive a dose of study intervention. Participants will be analyzed according to the product they actually received.

Participant Analysis Set	Description
PK Concentration	All participants randomly assigned to study intervention and who receive a dose of study intervention and in whom at least 1 plasma concentration value is reported.
PK Parameter	All participants randomly assigned to study intervention and who receive a dose of study intervention and have at least 1 of the PK parameters of interest calculated.

## 5. GENERAL METHODOLOGY AND CONVENTIONS

The analyses will be performed after database lock following dataset release after the last participant last visit.

### 5.1. Hypotheses and Decision Rules

There are no formal hypothesis tests planned for this study and no statistical decision rules will be applied.

### 5.2. General Methods

Unless specified otherwise, summaries will be produced by treatment.

#### 5.2.1. Analyses for Continuous Endpoints

Unless otherwise stated, continuous variables will be presented using summary statistics: number of observations, arithmetic mean, standard deviation, median, minimum and maximum values.

Log transformed continuous variables will be presented using summary statistics: number of observations, arithmetic mean, median, cv%, standard deviation, minimum, maximum, geometric mean and geometric cv%.

#### 5.2.2. Analyses for Categorical Endpoints

Categorical variables will be presented using summary statistics: number of observations and percentages.

### 5.3. Methods to Manage Missing Data

For the analysis of safety endpoints, the sponsor data standard rules for imputation will be applied.

#### 5.3.1. Concentrations Below the Limit of Quantification

In all PK data presentations (except listings), concentrations below the limit of quantification (BLQ) will be set to zero.

CCI

In listings, BLQ values will be reported as “<LLQ”, where LLQ will be replaced with the value for the lower limit of quantification.

### **5.3.2. Deviations, Missing Concentrations and Anomalous Values**

For PK **CCI** summary tables and plots of median profiles, statistics will be calculated having set concentrations to missing if 1 of the following cases is true:

1. A concentration has been collected as ND (ie not done) or NS (ie no sample),
2. A deviation in sampling time is of sufficient concern or a concentration has been flagged anomalous by the pharmacokineticist/statistician.

Note that summary statistics will not be presented at a particular time point if more than 50% of the data are missing.

### **5.3.3. Pharmacokinetic **CCI** Parameters**

Actual PK **CCI** sampling times will be used in the derivation of PK **CCI** parameters.

If a PK **CCI** parameter cannot be derived from a participant's concentration data, the parameter will be coded as NC (ie not calculated). (Note that NC values will not be generated beyond the day that a participant discontinues.)

In summary tables, statistics will be calculated by setting NC values to missing; and statistics will be presented for a particular dose with  $\geq 3$  evaluable measurements.

If an individual participant has a known biased estimate of a PK **CCI** parameter (due for example to an unexpected event such as vomiting before all the compound is adequately absorbed in the body), this will be footnoted in summary tables and will not be included in the calculation of summary statistics or statistical analyses. For PK parameter calculations, the sponsor standard rules will be applied.

## **6. ANALYSES AND SUMMARIES**

### **6.1. Primary Endpoint(s)**

#### **6.1.1. Adverse Events**

Adverse events will be listed and summarized by treatment, in accordance with sponsor reporting standards using the safety population defined in Section 4.

#### **6.1.2. Clinical Safety Laboratory Tests**

Laboratory data will be listed and summarized by treatment, in accordance with the sponsor reporting standards using the safety population defined in Section 4. Baseline is as defined in Section 3.1.2.

#### **6.1.3. Vital Signs**

Absolute values and changes from baseline in supine, standing and postural changes for systolic and diastolic BP and pulse rate will be listed and summarized by treatment and timepoint,

according to sponsor reporting standards, using the safety population defined in Section 4. Tables will be paged by parameter. Baseline is as defined in Section 3.1.3.

Mean changes from baseline for supine, standing and postural changes for systolic and diastolic BP and pulse rate will be plotted against time post-dose. On each plot there will be one line for each treatment. Data from all cohorts will be plotted on the same figure using a single line for the pooled placebo. Corresponding individual plots of changes from baseline will also be produced for each treatment.

Maximum decrease from baseline for supine and standing systolic and diastolic BP, maximum increase from baseline for standing and supine pulse rate, and maximum increase from baseline for postural differences (in systolic and diastolic BP, and pulse rate) will be summarized by treatment, according to sponsor reporting standards.

Maximum/minimum absolute values and changes from baseline for vital signs (for supine, standing and postural) will also be summarized descriptively by treatment using categories as defined in [Appendix 2](#). Numbers and percentages of participants meeting the categorical criteria will be provided. All planned and unplanned post-dose timepoints will be counted in these categorical summaries. All values meeting the criteria of potential clinical concern will be listed.

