1.3. Schedule of Activities

The SoA table provides an overview of the protocol visits and procedures. Refer to the STUDY ASSESSMENTS AND PROCEDURES section of the protocol for detailed information on each procedure and assessment required for compliance with the protocol. The investigator may schedule visits (unplanned visits) in addition to those listed in the SoA table, in order to conduct evaluations or assessments required to protect the well-being of the participant.

Visit Identifier ^a	Screening	Period 1 to Period 4 ^b						Foll	ET/DC											
	Day -28	Day	Day Day 1 Day Day							Visit:	Contact:									
	to Day -2	-1						-								2	3	Day	28-35	
Hours After Dose			0 ^d	0.17	0.5	1	1.5	2	4	6	8	10	12	16	24	36	48	8±2°	Days ^c	
Informed consent and demography	Х																			
Outpatient visit	Х																	Х		
Inpatient stay at CRU		Х	\rightarrow	\rightarrow	\rightarrow	\rightarrow	\rightarrow	\rightarrow	\rightarrow	\rightarrow	\rightarrow	\rightarrow	\rightarrow	\rightarrow	\rightarrow	\rightarrow	Xe			
Review inclusion/exclusion criteria	Х	Xf																		
Medical/medication history	Х	Xf																		
History of alcohol, tobacco, and illegal drug use	Х	Xf																		
Contraception check ^g	Х	Х															Х	Х	Х	Х
COVID-19 questionnaire ^h	Х	Х																		
COVID-19 test ⁱ	Х	Х																Х		
COVID-19 body temperature check	Х	Х	Х										Х		Х	Х	Х	Х		Х
Physical exam (height and weight at Screening	Х	Х																		
only) ^j																				
Neurological examination		Х	Х					Х	Х		Х							Х		Х
Review concomitant treatments	X	Х																Х	Х	Х
Respiratory rate			Х		Х		Х		Х		Х		Х		Х		Х			Х
Oral body temperature			Х		Х		Х		Х		Х		Х		Х		Х			
12-Lead ECG ^k	X		Х		Х	Х	Х	Х	Х	Х	Х		Х		Х		Х	Х		Х
Supine BP and PR	Х				Х	Х		Х	Х		Х		Х		Х		Х	Х		Х
Orthostatic (supine and standing) BP and PR			Х				Х			Х										
Continuous cardiac telemetry ¹			Х	\rightarrow	Х															
CCI																				
Serious/nonserious AE monitoring	Х	\rightarrow	\rightarrow	\rightarrow	\rightarrow	\rightarrow	\rightarrow	\rightarrow	\rightarrow	\rightarrow	\rightarrow	\rightarrow	\rightarrow	\leftarrow	\rightarrow	\rightarrow	\rightarrow	\rightarrow	Х	Х
Blinded study intervention administration ^o			Хр																	
Blood Samples for:																				
Clinical safety laboratory tests, including lipid	Х	Х													Х		Х	Х		Х
panel ^q																				

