Visit Identifier ^a	Screening		Period 1 to Period 4 ^b Follow-Up ET								ET/DC									
	Day -28	Day						Day	1						D	ay	Day	Visit:	Contact:	
	to Day -2	-1						-								2	3	Day	28-35	
Hours After Dose			0 ^d	0.17	0.5	1	1.5	2	4	6	8	10	12	16	24	36	48	8±2°	Days ^c	
Serum FSH ^r	Х																			
HBcAb, HBsAg, HBsAb, HCVAb, HIV testing	Х																			
Pfizer Prep B2 banked sample ^s			Х																	
Pfizer Prep D1.5 banked sample ^s			Х																	
PF-07258669 plasma pharmacokinetics			Х	Х	Х	Х	Х	Х	Х	Х	Х		Х	Х	Х	Х	Х			Х
CCI																				
Urine Samples for:																				
Urine drug test	Х	Х																		
Clinical safety laboratory tests ^q	Х	Х													Х		Х	Х		Х
Abbreviations: \rightarrow = ongoing/continuous event; AE = adverse event; BP = blood pressure; CRU = clinical research unit; DC = discontinuation; ECG = electrocardiogram;																				
ET = early termination; FSH = follicle stimulating hormone; HBcAb = hepatitis B core antibody; HBsAb = hepatitis B antibody; HBsAg = hepatitis B surface antigen;																				
HCVAb = hepatitis C antibody: HIV = human immunodeficiency virus: PR = pulse rate.																				

a. Day relative to start of study treatment (Day 1).

b. There will be a washout interval of ≥ 7 days between doses within an individual participant.

- c. Onsite follow-up visit to occur on Day 8 ±2 days in Period 4 only. Follow-up contact may occur via telephone contact and must occur 28-35 days after administration of the final dose of study intervention.
- d. Day 1 activities at time=0 hours are prior to the dose, except for study treatment administration.
- e. Participants may be confined to the CRU after completion of Day 3 activities at the discretion of the investigator or if safety, tolerability, or PK data dictate the need to prolong confinement in the CRU.
- f. Period 1 only. Review any changes from Screening.
- g. Contraception only required for male study participants and is recommended for partners of male study participants who are WOCBP.
- h. COVID-19 questionnaire includes check for suspected contact, risk zone, and COVID-19 related symptoms.
- i. Testing for active COVID-19 infection via testing for SARS-CoV-2 viral dosing (using PCR). To meet PCRU practice, testing for active COVID-19 infection will be performed at screening, admission, and follow-up visit.

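### By-treatment extremes and category counts for supine BP, pulse and ECG include a late visit that only the Period 4 dose has, which slightly favours flags at that dose

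*SAP*

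**What the plan says.** **Schedule.** The protocol's Schedule of Activities (1.3) marks the 12-lead ECG, supine BP and pulse, and safety laboratory tests at the on-site follow-up visit. Footnote c ties that visit to one period: "Onsite follow-up visit to occur on Day 8 ±2 days in Period 4 only".

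**Vital signs.** SAP 3.1.3 takes maxima, minima and largest changes over all post-dose measurements. SAP 6.1.3 summarizes them by treatment and says of the category counts: "All planned and unplanned post-dose timepoints will be counted in these categorical summaries". It gives no upper time limit.

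**ECG.** SAP 3.1.5 defines the endpoint as "The maximum increase from baseline over all measurements taken post-dose for QTcF, PR and QRS values". Protocol 9.4.1.1 tabulates each participant's largest post-dose QTcF value and largest increase by treatment. Neither gives a time limit.

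**Laboratory tests.** SAP 6.1.2 says only: "Laboratory data will be listed and summarized by treatment, in accordance with the sponsor reporting standards". It does not state which post-dose samples count.

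**Baselines.** SAP 3.1.2, 3.1.3 and 3.1.5 reset the baseline in every period from that period's own pre-dose values.

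**The concern.** A maximum taken over more values can only stay the same or grow, and a participant measured more often has more chances to cross a threshold. If one dose group is measured more often and over a longer time than the others, its extremes and category counts are not on the same footing.

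Here the extra opportunity falls on the last dose of each cohort. Protocol 4.3.3 plans each step relative to the highest dose given so far, so the last dose is normally the cohort's highest. Nothing in Periods 1 to 3 offsets this, because the next pre-dose values become the next period's baseline and do not count as late values of the earlier dose.

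The measures concerned are primary endpoints, read across doses and against pooled placebo with about 6 active participants per dose, so one flagged participant is 1/6, or 17 percentage points. Some thresholds are within reach of healthy volunteers: screening excludes a diastolic BP of 90 mm Hg or more, and the SAP Appendix 2 category starts at the same 90.

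**Working it through.** **1. Design counts.** 3 cohorts × 8 = 24 participants, as the protocol states. Per cohort, 6 active × 4 periods = 24 administrations = 8 participants × 3 active doses. Likewise 2 placebo × 4 periods = 8 administrations = 8 participants × 1 placebo dose. The plan's figures reproduce.

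**2. Timing of the extra visit.** Dosing is on Day 1, so Day 8 ±2 is Day 6 to Day 10, or 5 to 9 days (120 to 216 h) after dosing. The last scheduled post-dose assessment in Periods 1 to 3 is at 48 h.

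**3. Scheduled post-dose sets, counted from the Schedule of Activities.**

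| Measure | Times through 48 h | Periods 1–3 | Period 4 |
|---|---|---|---|
| ECG | 0.5, 1, 1.5, 2, 4, 6, 8, 12, 24, 48 h | 10 | 11 |
| Supine BP/pulse | 0.5, 1, 2, 4, 8, 12, 24, 48 h, plus 1.5 and 6 h from the orthostatic row | 10 | 11 |
| Laboratory | 24, 48 h | 2 | 3 |

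The orthostatic times count because SAP 3.1.3 says: "Note that some of the supine BP and pulse rate measurements are collected as part of the orthostatic assessment". Standing and postural BP, respiratory rate and oral temperature are not scheduled at the visit.

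**4. Who has the extra set.** All 6 participants on the Period 4 dose are scheduled for it, as is no one on a Period 1 to 3 dose and 2 of 8 placebo administrations per cohort (25%).

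**5. Chance of at least one flag, no drug effect.** Let p be the chance that a single measurement is flagged. The documents give no value, so p is assumed. With independent measurements, P(any flag) = 1 − (1 − p)^k. One more measurement adds p(1 − p)^k.

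| p (assumed) | ECG or supine BP, k = 10 | k = 11 | Excess per 6 | Laboratory, k = 2 | k = 3 | Excess per 6 |
|---|---|---|---|---|---|---|
| 0.005 | 4.9% | 5.4% | 0.03 | 1.0% | 1.5% | 0.03 |
| 0.02 | 18.3% | 19.9% | 0.10 | 4.0% | 5.9% | 0.12 |
| 0.05 | 40.1% | 43.1% | 0.18 | 9.8% | 14.3% | 0.27 |
| 0.10 | 65.1% | 68.6% | 0.21 | 19.0% | 27.1% | 0.49 |

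The relative excess is 5–10% for ECG and BP, and 43–50% for laboratory tests. The laboratory columns apply only if every post-dose sample is counted. For ECG and BP, p(1 − p)^10 peaks at p = 1/11, where it is 0.035. Under this model the excess therefore never passes 0.035 × 6 = 0.21 participants.

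Pooled placebo is 0.75 × the k = 10 value plus 0.25 × the k = 11 value. At p = 0.02 that is 0.75 × 18.3% + 0.25 × 19.9% = 18.7%, against 19.9% for the Period 4 dose.

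**6. A BP example.** Assume independent normal changes with SD 7 mm Hg. The Appendix 2 diastolic threshold is a change of 20 mm Hg. The chance of reaching it at least once is 2.1% with 10 values and 2.3% with 11, an excess of about 0.01 of 6 participants. If the outpatient value had SD 12 mm Hg (assumed), the 2.3% becomes 6.8%, an excess of (6.8% − 2.1%) × 6 = 0.28 participants. At the systolic threshold of 30 mm Hg the same models give 0.009% with 10 values, and 0.01% to 0.63% with 11.

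**7. Size of the extreme itself.** A simulation of the largest change from baseline used 8 values on the dosing day, 2 on later days and 1 at the visit. Between 0% and 70% of within-person variance was placed between days (assumed). The mean maximum rises by 0.05 to 0.11 within-person SD for ECG and BP. At the 70% share, the chance of exceeding 3 SD goes from 3.2% to 4.5%. With 2 versus 3 laboratory samples the mean maximum rises by about 0.28 SD.

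**The case against.** The strongest reply is that the supported part is too small to matter. Chance variation among 6 participants swamps an expected excess of 0.2, and the study has no hypothesis tests or statistical decision rules. That stands as to size, and it makes the point minor.

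The SAP also describes the largest change as taken within the period concerned, and the schedule places the visit under a follow-up heading. One could read this as excluding Day 8. It does not settle the matter: footnote c puts the visit in Period 4, and the vital-sign category rule admits every post-dose time point.

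A third reply is that counting late values toward the last dose is a cautious choice in a first-in-human study and matches the SAP 3.1.1 rule that assigns follow-up adverse events to the most recent dose. This is fair, and it is a reason to keep the late values visible. It does not make unequal windows comparable.

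Finally, a reader can trace a Day 8 flag, because vital signs and ECG are tabulated by timepoint and qualifying values are listed. That too stands, but the by-treatment counts would still combine unequal windows.

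Three stronger readings are tempting, and the documents do not support them:

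- **That the last dose will show more abnormalities by construction.** Only the chance is raised. The observed count may be equal or lower.
- **That laboratory incidence is inflated by about half.** The all-post-dose rule is written for vital signs and ECG. For laboratory tests the SAP defers to standards the documents do not contain.
- **That the artefact forms a rising dose trend or distorts escalation.** Doses may be modified or repeated (protocol 4.2), and the extra visit falls only at each cohort's Period 4 dose. The minimum safety review for escalation is through 48 h (protocol 6.6.1), before the visit.

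**Conclusion.** The point holds as a minor one. The SAP compares supine BP, pulse and ECG extremes, and the vital-sign categories, over windows that differ by dose. Each cohort's Period 4 dose has one extra scheduled set, and placebo shares only a quarter of that extra opportunity.

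For ECG and BP the excess is about 0.2 of 6 participants or less over most assumed rates. It goes somewhat above that only if outpatient values are assumed to be much more variable. These figures assume no drug effect and, outside the simulation, independent measurements; the per-measurement rates and SDs are also assumptions.

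The laboratory effect is conditional on an unstated rule. By-timepoint summaries, mean plots, standing and postural measures, respiratory rate and temperature are not affected by the visit. An early-termination visit can add late values in the same way to whichever dose a participant received last.

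**What to change.** In SAP 3.1.3, 3.1.5, 6.1.3 and 6.1.5, base the dose and pooled-placebo comparison of extremes and category counts on the window every period shares: dosing through 48 h, unscheduled values included. State the same window for laboratory abnormality incidence in 6.1.2. Scheduled sets are then equal at every dose (ECG 10, supine BP/pulse 10, laboratory 2), and the excess from scheduled values is zero.

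Show Day 8 and early-termination values in a separate follow-up summary, or keep the all-post-dose table beside the common-window one. Continue to list every value that meets the concern criteria, whenever it was taken.

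The cost is a few sentences, a time filter and one extra table. The downside is that a delayed finding appears in the follow-up or all-post-dose summary instead of the common-window comparison. Data collection does not change and no safety data are lost.
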